5.8 Extent of Treatment and Compliance

Extent of treatment will be listed by subject and summarized by treatment group.

A listing of device programming and settings will also be provided.

5.9 Subject Disposition

The number of subjects enrolled, treated, and discontinued before study end will be summarized by count and percentage for each treatment group.

5.10 Demographic and Baseline Characteristics

Demographic and Baseline characteristics will be presented for all subjects and for each analysis population as total enrolled and by treatment group. Gender, race, and ethnicity will be summarized by count and percentage. Age, height, body weight, and BMI, will be presented with numeric descriptive statistics.

The subject's age is calculated as the number of years from the subject's date of birth to the date the Informed Consent signed:

$$\text{Age} = [\text{Date Informed Consent Signed} - \text{Date of Birth}] / 365.25$$

Demographic and Baseline Characteristics will be summarized for the ITT, PP, and Safety populations, should these populations be different. All subjects who undergo surgery will be included in the safety population, with all adverse event and safety information reported.

5.11 Medical History

Medical History data will not be tabulated but will be provided in a listing by treatment group and subject.

5.12 Efficacy Analyses

The primary efficacy endpoint will be the UE Fugl-Meyer Assessment (FMA UE) with focus on the change from Visit 4 (baseline), to Visit 5 (Day 1 post in-clinic therapy). An analysis of covariance (ANCOVA) model will be used, with the change from baseline as the dependent variable, and the treatment, region, treatment by region interaction as factors, with age and baseline FMA UE score as covariates. The treatment by region interaction will be removed if $p > 0.10$.

In addition, as a sensitivity analysis of the FMA UE data across all visits, a Mixed Model Repeated Measures (SAS PROC MIXED) analysis will be used to evaluate the differences between treatment from Visit 4 through Visit 7 (end of Stage I). An unstructured covariance structure will be assumed, with the same factors and covariates as in the ANCOVA. This mixed model will also allow for missing data assuming missing at random.

Secondary Endpoints

1. FMA UE Responder at Day 90 - A responder analysis will be performed for the UE Fugl-Meyer with the definition of response defined as ≥ 6 point change from Baseline (Visit 4) to Visit 7 (Stage I). The proportion of subjects in each treatment group that meet or exceed the Responder definition will be determined and summarized by visit, including a 95% binomial confidence interval. Responder rates will be tested for differences between treatment groups using logistic regression, with treatment and randomization strata as factors. Other cut-off points for classification as a responder will be considered for a sensitivity analysis.
2. WMFT Change from baseline to Day 90 - This analysis will be based on the change in WMFT score from Baseline (Visit 4) to Day 90 (Visit 7). This will be done using ANOVA, with treatment and randomization strata as factors. Sensitivity analysis will not be done.

3. FMA UE Change from Baseline to Day 90 - This analysis will be done using the same model as for the primary endpoint, but with the change from Baseline to Day 90 as the dependent variable.

Other Endpoints

The QOL assessments, BDI and Motor Activity Log will be summarized by treatment group for each visit at which the assessment is collected, as well as the change from baseline to each visit. Because of the large number of assessments and domains, only summary statistics will be presented.

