3.1 Randomization

Subjects will be randomized 1:1 on the day of implant surgery to either the device treatment (rehabilitation and VNS) or control (rehabilitation and Control VNS) groups. An approved, unblinded person at each site accesses the subject's group assignment via an electronic (web-based) system.

Randomization will be stratified by FMA-UE score (20 to ≤ 35 ; >35 to 50), and age (≤ 30 , >30), within each region (North America vs ROW). Therefore, there are eight (8) randomization assignment tables. When a study site (linked to a region) submits the Randomization form with the subject's FMA-UE score, age, the Clinical Discovery Platform (CDP) will assign the next available treatment assignment from the corresponding randomization table.

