3.3 Study Schedule and Treatment

Stage I: Subjects will be screened and assessed for upper limb paresis associated with stroke using a detailed stroke history evaluation (including type, location, onset, neurological evaluation, etc.) and various assessment scores to determine the level of disability in performing everyday tasks. Clinical evaluations by a stroke expert will confirm subjects entering the study exhibit a moderate to severe motor impairment in the upper extremity (UE) (as indicated by a FMA-UE score of 20 to 50) and have at least a nine-month history of the disorder. After informed consent signature, repeat assessments and other measurements will be recorded prior to randomization. Subjects will maintain their group assignments through Visit 7 (end of Stage I, assessment follow-up).

Subjects will start study therapy after an approximately one-week recovery period after surgery. This time period may vary depending on schedules and subject recovery times. The assessments after surgery, and before treatment (Visit 4) will be the baseline for statistical analyses. After a 6 week acute treatment period, post treatment assessments will be done at Visit 5 (1 Day post treatment), Visit 6 (30 Days post treatment), and Visit 7 (90 Days post treatment). During this 90 day post treatment period, subjects will not receive in-clinic rehabilitation, but are given a magnet to swipe just prior to performing their in-home rehabilitation for 30 minutes daily. The magnet activates VNS in the VNS group subjects but does not activate VNS in the Control subjects.

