3.4 Sample Size Calculation/Justification

The study plan is to enroll and implant up to 120 subjects in order to have approximately 100 subjects complete the study. A sample size of 100 subjects total (50 per group) will have 80% power with 0.05 alpha to detect a difference of 2.3 with SD=4.0 on the FMA UE scale between the two treatment groups. This is based on the assumption of VNS having an average improvement of 7.5 from baseline, with control having an average change of 5.2 from baseline. A sample size of 50 per group will have over 95% power at 0.05 alpha to show a difference in responders (defined as an improvement of 6 points or more from baseline), assuming 75% response in the VNS group and 33% in the control group. With respect to safety, a sample of at least 100 subjects implanted and receiving VNS allows adequate power to detect the incidence of safety and device events. A sample of 100 subjects yields 95% probability that the study will reveal at least one occurrence of all events or complications that occur in subjects at a rate of 3% or greater. In addition, implantation and follow-up of 100 subjects for 6 weeks will yield 4200 subject-days (600 weeks or over 11 years) of total exposure.

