5.4 Study Hypothesis Testing

The primary objectives are to assess the efficacy and safety of 6 weeks of VNS therapy performed during rehabilitation for subjects with upper limb motor deficits following stroke. .

The primary efficacy analysis will be based on the change of the FMA UE score from baseline (Visit 4) to Visit 5 (Day 1 post therapy). The null hypothesis is the change in FMA UE is not different between VNS treatment and control sham treatment, with significance at alpha 0.05 two sided.

Three secondary endpoints will each be tested for significance with 0.05 Type I error (two sided) in a hierarchical manner. Significance will be declared for the first secondary endpoint at 0.05 only if the primary is significant at 0.05, and each subsequent endpoint only if all higher ranked endpoints were significant at 0.05.

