5.5 Handling of Missing Values and Outliers

All data collected under this protocol will be included in the assessment of safety. For AEs missing severity and relationship, if there is no other information available, relationship will be assessed as “possible” and severity will be assessed as “severe” for summary purposes, unless there is specific justification presented to impute other values. Missing or incomplete start dates will be imputed to the date of device implantation. Outliers that may have undue influence on the analysis and results will be discussed, but the results will not be based on any exclusion.

For the analysis of the efficacy endpoints, missing data will be imputed with a Last Observation Carried Forward approach. For any missing Visit 4 baseline data; the Visit 2 measure will be used as baseline. Multiple imputation, with missing at random assumptions using SAS PROC MI will also be performed as a sensitivity analysis. Data from the control group will be used to impute the missing in the VNS group. The specific imputation model will be defined prior to database lock. For the responder analysis, subjects with missing results will be imputed as non-responders for the initial evaluation, and a tipping point analysis will be used to assess sensitivity to missing data.

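### The primary and Day 90 FMA-UE models omit the pre-randomization FMA-UE score used for stratification: a modest, nearly free gain in precision forgone, not a bias

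*SAP*

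**What the plan says.** - **Stratification (SAP 3.1).** "Randomization will be stratified by FMA-UE score" in two bands (20 to 35, above 35 to 50), and by age and region. Allocation is on the day of implant, from a form that carries the subject's FMA-UE score and age.
- **Pre-randomization data (3.3).** Entry requires an FMA-UE of 20 to 50, and "repeat assessments and other measurements will be recorded prior to randomization".
- **Analysis baseline (3.3, 4.4, 5.3).** Visit 4, after surgery and before therapy.
- **Primary model (5.12).** Change from Visit 4 to Visit 5 is the outcome; treatment, region and their interaction are factors, "with age and baseline FMA UE score as covariates". The Day 90 FMA-UE analysis uses the same model, and the MMRM the same factors and covariates.
- **Other secondary models (5.12).** The responder logistic regression and the WMFT ANOVA include the randomization strata.
- **Stated use of the earlier reading in the efficacy analysis (5.5).** "For any missing Visit 4 baseline data; the Visit 2 measure will be used as baseline".

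**The concern.** Of the three stratification factors, age and region enter the primary model directly. For the third, a later reading stands in for the score actually used, and neither that score nor its band appears. Section 5.2 carries the region stratification through to the model, and two of the three secondary models carry all the strata, so the primary model follows the design less closely than they do. No reason is given.

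The practical question is whether Visit 4 makes the earlier score redundant. It would if FMA-UE were measured without error. With error, adjusting for a single reading only partly adjusts for the subject's true level, and a second reading improves that adjustment. What is at stake is the width of the interval for the primary treatment difference, in a trial where every subject undergoes surgery and planned power is close to its 80% target.

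**Working it through.** **Inputs from the SAP.** Test "with significance at alpha 0.05 two sided" (5.4). From 3.4: "A sample size of 100 subjects total (50 per group) will have 80% power with 0.05 alpha". The same sentence sets the target effect at 2.3 points and the SD at 4.0. The arm means behind that effect are "VNS having an average improvement of 7.5 from baseline, with control having an average change of 5.2 from baseline". The difference is 7.5 − 5.2 = 2.3.

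**The plan's own figure.** Noncentrality = 2.3 / (4.0 × √(2/50)) = 2.3 / 0.8 = 2.875. Power is Φ(2.875 − 1.96) = 0.820 by the normal approximation and 0.812 by noncentral t. The stated 80% reproduces.

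**Assumed, because the SAP does not give them.** Measurement-error SD *e* of a single FMA-UE score; between-subject true-score variance T = 64 (SD 8); SD *b* of true change between the pre-randomization reading and Visit 4, taken to persist to Visit 5. The change variance is held at the SAP's 4.0² = 16, so the variance of true gain is G = 16 − 2e².

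**Formulas.**
- Visit 4 only: residual variance = G + e² + S·e²/(S + e²), with S = T + b².
- Visit 4 plus the earlier score: residual variance = G + e² + P·e²/(P + e²), with P = T·e²/(T + e²) + b².

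**Worked case, e = 2, b = 0.** G = 16 − 8 = 8. Visit 4 only: 8 + 4 + 64×4/68 = 15.76. With both: P = 3.765, so 8 + 4 + 3.765×4/7.765 = 13.94. Reduction = 1 − 13.94/15.76 = 11.6%.

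**Results at 50 per arm** (power by noncentral t, 95 and 94 df; equivalent extra subjects per arm = 50 × (ratio of the two variances − 1)):

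| e | b | Visit 4 only | Both | Reduction | Power | Extra per arm |
|---|---|---|---|---|---|---|
| 0.5 | 0 | 16.00 | 15.88 | 0.8% | 0.812 → 0.815 | 0.4 |
| 1 | 0 | 15.98 | 15.50 | 3.1% | 0.813 → 0.824 | 1.6 |
| 2 | 0 | 15.76 | 13.94 | 11.6% | 0.818 → 0.862 | 6.5 |
| 2.5 | 0 | 15.44 | 12.73 | 17.6% | 0.826 → 0.891 | 10.7 |
| 1 | 2 | 15.99 | 15.83 | 1.0% | 0.813 → 0.816 | 0.5 |
| 2 | 2 | 15.78 | 14.64 | 7.2% | 0.817 → 0.845 | 3.9 |
| 2.5 | 2 | 15.47 | 13.55 | 12.4% | 0.825 → 0.871 | 7.1 |

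With b = 3 the reductions for e = 1, 2 and 2.5 are 0.5%, 4.7% and 8.8%. True-score SDs of 6 or 10 change the figures little (for e = 2, b = 0: 10.9% and 11.9%). The ceiling is e² = 8, where all of the change variance is measurement error: 22% at T = 64.

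**Simulation.** 3,000 runs per setting, 100 subjects, entry limited to 20 to 50, stratified blocks, b = 0. Adding the continuous score moved power from 0.804 to 0.822 (e² = 2), 0.823 to 0.854 (e² = 4) and 0.847 to 0.905 (e² = 8), with no gain at e² = 0.5. Adding only the two-level band gave less: 0.847 to 0.862 at e² = 8. Type I error was between 0.043 and 0.051 in every model.

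**The case against.** The strongest reply is that nothing is broken. The model already adjusts for a continuous FMA-UE score taken just before therapy, plus age and region. Planned power is reached and type I error is sound, so a second reading is a refinement. That stands, and it fixes the grade of the point.

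The size is also open to challenge. The SAP gives no test-retest error, between-subject SD or correlation between the two readings, and surgery with about a week of recovery falls between them. Assuming no true change in that interval is the favourable case. This stands too, which is why the rows with b = 2 are shown.

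Two stronger readings are tempting and are not supported:
- A reader might infer that a baseline taken after allocation biases the primary test, and that the added covariate would protect against this. Section 3.2 assigns assessments to a blinded assessor who does not treat that subject, both arms are implanted, and Visit 4 precedes therapy. Nor would the covariate protect: Visit 4 would remain both in the endpoint and in the model.
- A reader might infer that Visit 4 error does special harm because Visit 4 is subtracted. With Visit 4 as a covariate, the treatment estimate and its standard error are the same whether the outcome is Visit 5 or the change. Only incomplete adjustment through an error-prone covariate remains.

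It would also be too strong to say that the earlier score is discarded: it governs entry and stratification, its bands enter two secondary models, and Visit 2 is the missing-baseline fallback.

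**Conclusion.** The point holds as a missed efficiency in the primary and Day 90 FMA-UE models. It is not a bias, a validity error or a shortfall in power.

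The direction is clear whenever FMA-UE carries appreciable measurement error. The size rests on assumptions: residual variance falls by about 3% to 18% (error SD 1 to 2.5, no true change between readings), by about 1% to 12% with a between-visit true-change SD of 2, and by close to nothing if error is very small. In power terms this runs from under half a point to about 6.5 points, starting from about 81% to 83%.

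That Visit 2 precedes randomization is an inference from 3.3 and 5.5. The Randomization-form score precedes it by construction, so the remedy should use that score.

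**What to change.** Before unblinding, amend 5.12 so that the primary ANCOVA and the Day 90 FMA-UE model include the continuous FMA-UE score submitted on the Randomization form as a covariate, beside Visit 4 FMA-UE, age and region. Keep change from Visit 4 as the endpoint. Use the continuous score, since the two-level band recovers much less. The MMRM inherits the term, because 5.12 ties its covariates to the ANCOVA.

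Add one clarification for subjects whose Visit 4 score is missing and replaced by Visit 2 under 5.5: the substituted value serves as the Visit 4 covariate, and the Randomization-form score stays in the model. The two may be the same number for such a subject, so the rule should be written down in advance.

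The cost is a sentence or two of SAP text and one degree of freedom. No new visits, subjects or data are needed.

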5.3 Efficacy Endpoints

The primary endpoint will be the change of the FMA UE score from Visit 4 (pre-therapy, baseline) to Visit 5 (Day 1 post therapy).

There are three hierarchical secondary endpoints

1. The proportion of responders, defined as a 6-point change or greater in the FMA UE score from baseline (Visit 4) to Day 90 post treatment (Visit 7)

2. The change in WMFT from baseline (Visit 4) to Day 90 post treatment (Visit 7)
3. The change in FMA UE score from baseline (Visit 4) to Day 90 post treatment (Visit 7)

Quality of Life Endpoints

Quality of life assessments and a motor activity log will be used to provide data to support overall treatment response:

- Stroke Impact Scale (SIS): The SIS has been developed to assess eight different domains of health-related quality of life, such as emotion, communication, memory, and thinking, and social role function. Each item is rated on a 5-point Likert scale in terms of the difficulty the person has experienced in completing each item. Scores for each domain range from 0-100.
- Stroke Specific QOL (SS-QOL): The SS-QOL is a self-report questionnaire consisting of 49 items in the 12 domains of energy, family roles, language, mobility, mood, personality, self-care, social roles, thinking, upper extremity (UE) function, vision, and work/productivity.
- 5Q-5D QOL (general QOL) – EQ-5D™ is a standardized instrument for use as a general measure of health outcome. It provides a simple descriptive profile and a single index value for health status.
- Motor Activity Log (MAL) - The MAL consists of 14 activities (patient reported outcomes) of daily living (ADLs) such as using a towel, brushing teeth, and picking up a glass. For a specified time period post-stroke, the individual is asked about the extent of the activity performed and how well it was performed by the more impaired arm. The response scale ranges from 0 (never used) to 5 (same as pre-stroke).

These QOL measures are considered “tertiary” or “other” endpoints that provide further evidence of the benefits of treatment (not considered primary or secondary endpoints).

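### WMFT change at Day 90, a gated secondary endpoint, is tested without adjustment for baseline WMFT, and its ban on sensitivity analysis conflicts with SAP 5.5

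*SAP*

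**What the plan says.** SAP 5.12 specifies the WMFT analysis in two sentences: "This will be done using ANOVA, with treatment and randomization strata as factors. Sensitivity analysis will not be done". The strata are those of SAP 3.1, formed by FMA-UE band, age band and region (eight cells). WMFT is not one of them.

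In the same section the primary endpoint is analysed by ANCOVA "with age and baseline FMA UE score as covariates", and the third secondary endpoint, Day 90 FMA-UE change, uses that same model.

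SAP 5.3 states "There are three hierarchical secondary endpoints" and puts WMFT change second. Under SAP 5.4 the first secondary endpoint is tested only if the primary succeeds, and "each subsequent endpoint only if all higher ranked endpoints were significant at 0.05".

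On missing data, SAP 5.5 says: "For the analysis of the efficacy endpoints, missing data will be imputed with a Last Observation Carried Forward approach". It then adds: "Multiple imputation, with missing at random assumptions using SAS PROC MI will also be performed as a sensitivity analysis". It sets a different rule for responders (non-response imputation and a tipping point analysis) but names no exception for WMFT.

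**The concern.** **Baseline adjustment.** An unadjusted change score assumes, in effect, that the slope of Day 90 WMFT on Visit 4 WMFT is 1. When the true slope differs, the change score carries variance that a baseline covariate would remove. The strata reach baseline WMFT only indirectly, mainly through its association with the FMA-UE band. The SAP gives no reason for treating WMFT differently from the two FMA-UE change analyses. Validity is not in question; the loss is in precision. It matters because of rank: if WMFT fails, Day 90 FMA-UE change cannot be claimed whatever its p-value.

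**Sensitivity analysis.** Sections 5.5 and 5.12 give opposite instructions for WMFT. If 5.12 prevails, LOCF becomes the only missing-data handling for a confirmatory Day 90 result. SAP 3.4 plans up to 120 implanted for about 100 completers, so up to 20/120 = 16.7% may not complete.

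**Working it through.** **The plan's own figure.** With 50 per group, difference 2.3, SD 4.0 and two-sided 0.05 (SAP 3.4), power is 82.0% by the normal approximation and 81.2% by the t distribution. The stated 80% reproduces. It concerns the primary FMA-UE comparison; the SAP gives no WMFT SD, effect, power or correlation.

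**Assumptions for WMFT.** Let ρ be the Visit 4–Visit 7 correlation, k the ratio of Visit 7 to Visit 4 SD, and c the baseline FMA-UE–WMFT correlation. Ranges are ρ = 0.5 to 0.9 and c = 0.5 to 0.7. The change-score test is assumed to have 80% power.

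**Without strata.** The variance of the ANCOVA estimate relative to the change-score estimate is

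k²(1 − ρ²) / (1 + k² − 2ρk).

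This never exceeds 1 and equals 1 only when ρk = 1. For example, at k = 1.2 and ρ = 0.833 both variances are 0.44. At k = 1 it reduces to (1 + ρ)/2. Power with the covariate is Φ((0.842 + 1.960)/√ratio − 1.960).

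**With strata in both models.** Take k = 1, a median-split FMA-UE stratum, and Day 90 WMFT related to FMA-UE only through baseline WMFT. The ratio is then

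(1 + ρ) / [(1 + ρ) + (1 − ρ)(1 − a²)], with a² = (2/π)c².

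This gives a² = 0.159 at c = 0.5 and 0.312 at c = 0.7. At ρ = 0.5 and c = 0.5, for example, 1.5/(1.5 + 0.5 × 0.841) = 0.781 and power is 0.887.

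| ρ | Ratio, no strata | Power, no strata | Power, with strata (c = 0.5 to 0.7) | Points forgone, with strata |
|---|---|---|---|---|
| 0.5 | 0.75 | 0.899 | 0.887 to 0.874 | 7 to 9 |
| 0.7 | 0.85 | 0.860 | 0.851 to 0.843 | 4 to 5 |
| 0.9 | 0.95 | 0.820 | 0.817 to 0.814 | 1 to 2 |

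**Simulation.** With 100 subjects, FMA-UE band and region in both models and 6,000 runs, ANOVA/ANCOVA power was:

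| Case | c = 0.5 | c = 0.7 |
|---|---|---|
| ρ = 0.5, k = 1 | 0.799/0.882 | 0.793/0.863 |
| ρ = 0.7, k = 1 | 0.796/0.844 | 0.802/0.840 |
| ρ = 0.9, k = 1 | 0.800/0.812 | 0.788/0.802 |
| ρ = 0.833, k = 1.2 (no gain expected) | 0.796/0.793 | 0.798/0.793 |

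Type I error (4,000 runs) was 0.046 to 0.055 for ANOVA and 0.045 to 0.055 for ANCOVA. Using all eight strata, the gains were about 6 to 8 points at ρ = 0.5, 3 to 5 at 0.7 and about 1 at 0.9. With 120 subjects and 10% of values carried forward, the gain at ρ = 0.7 was about 4 points.

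**A case tied to an SAP figure.** Suppose WMFT behaved like FMA-UE, with change SD 4.0 and an assumed baseline SD of 7 to 8.66 (the upper value is a uniform spread over the 20–50 entry range, 30/√12). With equal SDs, ρ = 1 − 16/(2·SD²), which is 0.837 at SD 7 and 0.893 at SD 8.66. The power forgone is about 2 to 3 points without strata and 1.5 to 2.8 with them.

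**Chance imbalance.** At 50 per arm, one SE of within-stratum baseline imbalance is √(2/50) × √(1 − a²) = 0.17 to 0.18 SD. It moves the change-score estimate by (1 − ρ) times that: 0.08 to 0.09 SD at ρ = 0.5, about 0.05 at 0.7 and 0.02 at 0.9.

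**Sensitivity rule.** No arithmetic applies. WMFT change is listed in 5.3 as an efficacy endpoint, so the imputation rule of 5.5 covers it. Section 5.12 excludes any sensitivity analysis for it, does not refer to 5.5 and claims no override.

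**The case against.** On the first point, the ANOVA is a valid, fully specified test, so this is a matter of efficiency and not an error. That stands. Chance imbalance is already reflected in the ANOVA standard error, so it is another face of the same precision loss and not a second defect. That stands too. The responder analysis also uses only treatment and strata, so WMFT is not alone in its model form; but the FMA-UE band in those strata is the responder endpoint's own baseline, so the parallel is partial.

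The magnitude rests on assumptions, the no-strata figures overstate the effect of the change, and the only scenario linked to an SAP number gives 1.5 to 2.8 points. This is fair, and the with-strata figures are the ones to use. The four-cell simulation is not the specified model and ignores carried-forward values, but the runs with all eight strata and with LOCF gave similar gains.

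On the second point, a specific rule can be read as overriding a general one, or the sentence as declining only extras such as alternative models or cut-offs. Neither reading is stated, and they lead to different programming. Writing an exception into 5.5 would also remove the contradiction. However, it would leave LOCF unchecked for a gated endpoint, whereas the responder endpoint has a tipping point analysis and FMA-UE change has multiple imputation and a mixed model.

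**Conclusion.** Both parts hold. Leaving out Visit 4 WMFT generally costs precision on the endpoint that gates Day 90 FMA-UE change. With strata in the model, equal SDs and 80% starting power, the cost is roughly 1 to 9 power points over ρ = 0.9 down to 0.5, and about 1.5 to 2.8 points if WMFT resembles FMA-UE. There is no gain where ρk = 1. Bias and type I error are not at issue.

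The contradiction between 5.5 and 5.12 depends on no assumption. As written, it is undetermined whether the WMFT result will be checked against the LOCF imputation. Both should be corrected before unblinding, because a covariate or sensitivity analysis added later would look data-driven. Confidence in the size of the first part is moderate, since the SAP supplies no WMFT figures.

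**What to change.** In SAP 5.12, keep treatment and the randomization strata and add one term, for example: *WMFT change (Visit 4 to Visit 7) is analysed by ANCOVA; factors are treatment and randomization stratum, and Visit 4 WMFT is the covariate.*

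Separately, delete the sentence excluding sensitivity analysis and state that the multiple-imputation analysis of 5.5 applies to WMFT.

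The cost is SAP wording, one residual degree of freedom and one more programmed analysis. With 100 subjects, eight strata and treatment, residual df is 100 − 8 − 1 = 91, falling to 90. No new data are needed. Where the covariate brings no gain, the simulated power loss was under 1 point.
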